5.7.2.2. Time to and Duration of Erythroid Response

Time to and duration of erythroid response will be analyzed for erythroid responders defined as below:

- For NTD patients, mean increase of ≥ 1.0 g/dL from pretreatment hemoglobin during any rolling 12 weeks

- For NTD patients, mean increase of ≥ 1.5 g/dL from pretreatment hemoglobin during any rolling 12 weeks
- For NTD patients, mean increase of ≥ 1.0 g/dL from pretreatment hemoglobin during any rolling 24 weeks
- For NTD patients, mean increase of ≥ 1.5 g/dL from pretreatment hemoglobin during any rolling 24 weeks
- For TD patients, $\geq 33\%$ reduction in RBC transfusion burden compared to pretreatment using 12-week intervals
- For TD patients, $\geq 50\%$ reduction in RBC transfusion burden compared to pretreatment using 12-week intervals
- For TD patients, $\geq 33\%$ reduction in RBC transfusion burden compared to pretreatment using rolling 24-week intervals
- For TD patients, $\geq 50\%$ reduction in RBC transfusion burden compared to pretreatment using rolling 24-week intervals

Time to erythroid response will be defined as the time from the first dose date to the first date of any rolling 12- or 24-week interval achieving above erythroid response.

Duration of erythroid response will be defined as the time from the starting date of the first rolling 12- or 24-week interval achieving response to the last date of the last consecutive rolling 12- or 24-week interval achieving response. When there are multiple disjointed intervals with response, the longest interval will be used. Patients with response ongoing by the analysis cutoff day will be censored.

Both time to and duration of erythroid response will be analyzed as continuous variables and summarized by descriptive statistics. In addition, duration of erythroid response will also be analyzed as a time to event endpoint.

The derivations of time to and duration of erythroid response will be listed for each patient.

Erythroid responders may experience multiple periods of response (≥ 8 weeks, ≥ 12 weeks, or ≥ 24 weeks). For these responders, the number of episodes and cumulative duration will be summarized by NTD and TD separately. As an exploratory analysis, the cumulative duration of the multiple responses will be analyzed using Kaplan-Meier method.

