- Change from baseline in hemolysis parameters, including total/indirect bilirubin, and LDH
- Change from baseline in iron overload and iron metabolism parameters, including serum iron, total iron binding capacity (TIBC), transferrin, calculated transferrin saturation, soluble transferrin receptor, ferritin, non-transferrin bound iron (NTBI), hepcidin, iron chelation therapy use and LIC by MRI

The exploratory endpoints will include evaluation of biomarkers related to the TGF- β superfamily, quality of life, change in EMH mass size, change in spleen size, change in BMD, change in leg ulcer size, and change in the 6MWT distance in NTD patients.

All binary endpoints will be summarized using both a point estimate and its exact confidence interval based on the binomial distribution. The time-to-event type secondary endpoints will be

analyzed using Kaplan-Meier method to estimate the survival curve and median time to event and 95% CI.

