5.7. Efficacy Analyses

No formal hypothesis testing is planned. All efficacy endpoint will be performed using the ITT population.

In general, the below rules apply to the derivations of efficacy endpoints which utilize hemoglobin and RBC transfusion data unless specified otherwise:

- Hemoglobin measurements within 14 days following RBC transfusion will be excluded from the efficacy analysis.
- For each patient, all efficacy endpoints will be derived based on an analysis cutoff day, defined as the last dose + 56 days or the last date from transfusion record data, whichever is earlier.

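### For patients with several response episodes, duration is taken from the longest while time to response uses the first, so the two endpoints can describe different episodes and the Kaplan-Meier median duration tends to lengthen with follow-up alone

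*SAP*

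**What the plan says.** SAP 5.7.2.2 defines time to response as "the time from the first dose date to the first date of any rolling 12- or 24-week interval" that meets the response criterion. It starts the definition of duration at the same place, as "the time from the starting date of the first rolling 12- or 24-week interval achieving response to the last date of the last consecutive" responding interval. The next sentence changes this for patients with more than one episode: "When there are multiple disjointed intervals with response, the longest interval will be used". On censoring it says: "Patients with response ongoing by the analysis cutoff day will be censored".

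On analysis: "Both time to and duration of erythroid response will be analyzed as continuous variables and summarized by descriptive statistics", and duration is in addition treated as a time-to-event endpoint. Protocol 15.2.3 states that time-to-event secondary endpoints are "analyzed using Kaplan-Meier method to estimate the survival curve and median time to event and 95% CI". The cutoff day is patient-specific: SAP 5.7 has it "defined as the last dose + 56 days or the last date from transfusion record data, whichever is earlier".

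SAP 5.7.2.2 itself foresees repeated periods of response. It plans summaries of the number of episodes and of cumulative duration, an exploratory Kaplan-Meier analysis of cumulative duration, and a per-patient listing of the derivations. It plans no summary of the first episode's duration. The protocol names duration of response as a secondary objective (8.2) and contains no longest-episode rule.

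**The concern.** A patient's longest episode is a maximum over the episodes seen so far. It cannot fall as data accrue, and it tends to grow with the number of episodes observed, which grows with follow-up. Dosing may run to Day 1825 (Protocol 10.1), and the cutoff differs by patient, so responders contribute maxima taken over very different observation times.

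Two consequences follow for patients with several episodes. First, time to response and duration form a natural pair (how soon, then for how long), but the duration may belong to a later episode than the one whose onset was timed. Second, a longer median at a later data cut could be read as better durability when only follow-up has changed. More than one cut is plausible: Protocol 15.4 foresees an analysis for registration filings, and both documents mention periodic review of response data.

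**Working it through.** The documents give no expected duration, episode count or gap length, so there is no plan figure to reproduce. The check holds patient behaviour constant, varies only follow-up, and compares the two definitions.

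**From the documents:** first-interval rule for time to response, longest-interval rule for duration, and censoring of ongoing responses (SAP 5.7.2.2); maximum dosing of 1825 days, 1825 / 7 = 260.7 weeks, run as 260 (Protocol 10.1).

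**Assumed:** everything about episodes.
- *Model A*, 20,000 patients per setting: response and non-response alternate. A response lasts 12 weeks plus an exponential time, and gaps are exponential. Settings are given as mean response / mean gap in weeks.
- *Model B*, 4,000 patients per setting: rolling 12-week windows moved weekly; response means at least 33% fewer units than a 12-week baseline. Transfusion is every 3 weeks, with units Binomial(4, 0.5 × (1 − r)) for a constant true reduction r.

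**Estimator:** S(t) = Π(1 − d/n) over event times up to t, where d is the number of episodes ending and n the number at risk. The median is the smallest t with S(t) ≤ 0.5. An episode still running at the cutoff is censored.

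Kaplan-Meier medians in weeks, at 48 / 96 / 156 / 260 weeks of follow-up common to all patients:

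| Setting | First episode | Longest episode | Ratio at 260 weeks |
|---|---|---|---|
| A 24/12 | 20.3 / 20.3 / 20.4 / 20.3 | 22.7 / 29.4 / 34.8 / 40.4 | 40.4 / 20.3 = 1.99 |
| A 36/12 | 28.5 / 28.8 / 28.6 / 28.7 | 31.5 / 42.3 / 52.1 / 62.8 | 62.8 / 28.7 = 2.19 |
| A 52/26 | 39.7 / 40.1 / 39.7 / 40.1 | 41.0 / 50.8 / 63.6 / 80.2 | 80.2 / 40.1 = 2.00 |
| A 104/26 | not reached / 77.1 / 75.6 / 77.4 | not reached / 91.1 / 107.4 / 136.8 | 136.8 / 77.4 = 1.77 |
| B, r = 33% | 23 / 23 / 23 / 23 | 29 / 38 / 43 / 47 | 47 / 23 = 2.04 |
| B, r = 20% | 20 / 20 / 19 / 19 | 23 / 26 / 29 / 35 | 35 / 19 = 1.84 |
| B, r = 0 | 17 / 17 / 17 / 17 | 18 / 20 / 23 / 23 | 23 / 17 = 1.35 |

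The first-episode median is flat and the longest-episode median rises. Across these settings, the longest episode is not the first in 2–29% of responders at 48 weeks, 30–74% at 156 weeks and 51–86% at 260 weeks. At 24 weeks the two definitions almost coincide.

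**Mixed follow-up.** The SAP cutoff is individual, so a common cutoff overstates the effect. Model A was repeated with exponential follow-up capped at 260 weeks, a 24-week mean gap and mean episodes of 24 to 156 weeks:
- mean follow-up 104 weeks: ratio about 1.3 to 1.5; the first episode is also the longest in 57–85% of responders;
- mean follow-up 52 weeks: ratio about 1.1 to 1.3; the first is the longest in 73–94%;
- all patients followed for 260 weeks: ratio about 1.6 to 2.1.

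**24-week definitions.** Four of the eight responder definitions in SAP 5.7.2.2 use 24-week windows. Raising the minimum episode to 24 weeks (mean 48 weeks, five years for all) lowers the ratio from about 2.1 to about 1.65.

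**Why censoring does not help.** As an illustration, take a patient whose 30-week episode has ended: an event at 30. If a later episode has reached 40 weeks and is ongoing at the next cut, the same patient becomes censored at 40, and the earlier event disappears. The SAP also leaves open how to code a patient whose longest episode has ended but who is responding again at cutoff.

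**The case against.** **The rule is open and partly covered.** It is stated plainly, derivations are listed per patient, and episode counts and cumulative duration are summarised. That stands as context. It does not supply a first-episode median, and counts and cumulative duration also grow with follow-up.

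**The first episode is not neutral.** This is the strongest objection. Dose is titrated from Cycle 3 when response is inadequate (Protocol 10.9), and data from the ascending-dose base study are included for direct rollovers (SAP 4.1). A first episode may therefore precede titration, and a later one may be longer because the dose changed. Administrative interruptions (Protocol 10.10) could also split a response. The simulations assume that all episodes of a patient come from one distribution. This stands, and it is a reason to keep the longest-episode result alongside.

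**Stakes are limited.** The primary objective is safety, there is no comparator, and SAP 5.2 plans no hypothesis testing. This also stands.

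A reader might infer more than the documents support:
- *That duration always describes a different episode.* It does not for single-episode responders, or where the first episode is the longest.
- *That the median will be about doubled.* That needs five years of follow-up for nearly everyone and mainly the 12-week definitions.
- *That it must rise at every data cut.* It is a tendency; the documents say only that repeated responses may occur.
- *That all growth in reported duration comes from this rule.* The uncensored descriptive mean would rise for first episodes too (Model A 36/12: 27.2 weeks at 48 weeks of follow-up, 36.0 at 260), because ongoing responses are cut short. The drift in the Kaplan-Meier median is what is specific to the rule.

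**Conclusion.** The point holds for responders with two or more disjoint episodes. For them, the paired endpoints can refer to different episodes, and the Kaplan-Meier median of the longest episode tends to increase with follow-up at constant durability. The direction was the same in every setting tried.

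The size rests on assumed episode and gap lengths. The ratio of longest to first median is about 1.1 to 1.5 with mixed follow-up averaging one to two years. With five years for all it is about 1.6 to 2.1 at a 24-week mean gap, and 1.35 to 2.19 across the tabulated settings. It is smaller for 24-week windows and exactly 1 if every responder has a single episode. What is affected is the reading of a named secondary endpoint. It should be changed before database lock.

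**What to change.** In SAP 5.7.2.2, define the duration-of-response analysis, including the Kaplan-Meier median, on the first response episode, the one that sets time to response, censored if still ongoing at the cutoff day. Keep the present result beside it, labelled *longest response episode*, with follow-up time stated and with a sentence saying that censoring refers to the episode being analysed. Retain the planned episode-count and cumulative-duration summaries.

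The cost is about a sentence or two of SAP text and a programming change, using data already collected. The downsides are that the headline median becomes shorter and that a first episode may precede dose titration; showing both results lets the reader see this.

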All binary endpoints will be summarized using both a point estimate and its exact CI based on the binomial distribution. The time-to-event type secondary endpoints will be analyzed using Kaplan-Meier method to estimate the survival curve and median time to event and 95% CI.

Anti-drug antibody analysis: The results of anti-drug and neutralizing antibody testing for ACE-536 and human ActRIIB protein versus time will be presented. Exploratory analysis will be performed on the potential effect of ADA on ACE-536 PK and drug exposure if ADA tests are deemed positive.

Pharmacokinetics analysis: PK parameters for ACE-536, such as maximum serum concentration (C_{max}), time to maximum concentration (t_{max}), and area under the concentration/time curve (AUC), will be estimated using non-compartmental and/or single compartment analysis, as appropriate. Dose proportionality may be assessed using the exposure data (e.g., C_{max} , AUC) if sufficient dose levels are studied. Descriptive statistics will

be provided for serum concentrations and PK parameters. The relationship between ACE-536 exposure and response (i.e., safety, efficacy, and biomarkers) may be explored, as appropriate.

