15.2.3. Secondary Analysis

All efficacy analyses will be performed for the EE and mITT populations.

Efficacy will be evaluated by determining the proportion of β -thalassemia patients who have an erythroid response, defined as 1) a mean hemoglobin increase ≥ 1.0 g/dL or ≥ 1.5 g/dL over an 8-week or 12-week period as compared to baseline, not influenced by RBC transfusion in NTD patients or 2) $\geq 20\%$ or $\geq 50\%$ reduction in RBC transfusion burden over an 8-week or 12-week period as compared to the 8-week or 12-week period pretreatment in TD patients.

Baseline hemoglobin for NTD patients will be the average of two or more measurements performed during the screening period for base study A536-04 (for patients without treatment

interruption) or study A536-06 (for patients with treatment interruption). Hemoglobin measurements within 2 weeks following RBC transfusion will be excluded.

Transfusion burden for TD patients will be defined as the ratio of RBC transfusion units (or mLs) transfused during an interval divided by the duration of that interval, where the interval may be during the pretreatment period or the treatment plus follow-up period. The interval during the pretreatment period will be defined as the 8 or 12 weeks prior to Cycle 1 Day 1 of base study A536-04 (will also be analyzed using pretreatment period of study A536-06 for patients with treatment interruption). An interval during the treatment plus follow-up period will be defined as an 8-week or 12-week interval after Cycle 1 Day 1 of study A536-06.

The erythroid response, as defined above, will also be evaluated using other pre-treatment and on-treatment intervals and other % reductions in RBC units transfused, including 100% (transfusion-free).

The erythroid response will be summarized using both a point estimate and its exact 95% CI based on binomial distribution.

No direct comparison testing with concurrent or historical controls will be performed.

Analysis of other secondary efficacy/PD endpoints will include:

- Time to erythroid response and duration of erythroid response
- Change/percent change from pretreatment in mean transfusion burden in TD patients
- Change in mean hemoglobin level in NTD patients
- Change in pre-transfusion hemoglobin levels in TD patients (including analysis of patient subset with < 20% change in transfusion burden)
- Change from baseline in erythropoiesis parameters, including EPO, reticulocytes, nucleated RBCs, and soluble transferrin receptor

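### Time to erythroid response is summarised in responders only, and the protocol's Kaplan-Meier analysis of it is not carried into the SAP or listed as a change

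*SAP*

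**What the plan says.** Protocol 15.2.3 names this item among the other secondary efficacy endpoints: "Time to erythroid response and duration of erythroid response". The synopsis gives the method, and 15.2.3 repeats it: "The time-to-event type secondary endpoints will be analyzed using Kaplan-Meier method to estimate the survival curve and median time to event and 95% CI".

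SAP 5.7.2.2 sets the analysis population with "Time to and duration of erythroid response will be analyzed for erythroid responders defined as below", using 12- and 24-week response definitions for NTD and TD patients. Time to response runs from first dose to the first day of a qualifying interval. The planned summary is "Both time to and duration of erythroid response will be analyzed as continuous variables and summarized by descriptive statistics", followed by "In addition, duration of erythroid response will also be analyzed as a time to event endpoint".

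The only censoring rule is in the paragraph on duration: "Patients with response ongoing by the analysis cutoff day will be censored". That paragraph also says "When there are multiple disjointed intervals with response, the longest interval will be used".

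SAP 4.1 and 5.7 assign all efficacy analyses to the ITT population. SAP 5.7 defines an analysis cutoff day: the earlier of last dose plus 56 days and the last transfusion record date. Protocol 15.5 says the SAP will indicate departures from the protocol's analyses. SAP 5.12.6 lists two major changes, the baseline hemoglobin definition and the removal of the EE population (with mITT renamed ITT). Time to response is not among them.

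**The concern.** Restricting time to response to responders conditions on the outcome. Everyone in the set has the event, so nobody is censored, and patients who were treated without responding drop out of the summary. The resulting median says how quickly responders responded. It does not say how long a treated patient can expect to wait, and it would be almost the same whether 40% or 80% responded. A reader who expects the protocol's Kaplan-Meier median could take it for that figure.

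Duration raises a smaller reporting issue. The SAP censors ongoing responses and also plans descriptive statistics of duration, without saying how censored values enter them.

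**Working it through.** The documents state no figure for this point, so there is none to reproduce. The check has a textual part and an illustrative part.

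**Text.** Time to response and duration are the only time-to-event items in the protocol's list of other secondary endpoints, so the plain reading of its Kaplan-Meier sentence covers both. The SAP keeps a time-to-event analysis for duration only. It gives non-responders no censoring time for time to response, and its restriction to responders departs from its own rule that efficacy uses the ITT population.

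**Effect of the response rate.** Assume a fraction p of patients can respond, with exponential response times and a median of 60 days among them. The rate is λ = ln 2 / 60 = 0.01155 per day. The responders-only median is about 60 days for any p. The all-patient median solves p(1 − e^(−λt)) = 0.5, so t = −ln(1 − 0.5/p)/λ.

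- p = 0.8: −ln(0.375)/0.01155 = 0.9808/0.01155 ≈ 85 days
- p = 0.6: −ln(0.1667)/0.01155 = 1.7918/0.01155 ≈ 155 days
- p = 0.4: 0.5/0.4 exceeds 1, so the median is not reached

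Simulation with 60% completing five years agreed: 59 days in responders at every p, against Kaplan-Meier medians of 85 days, 156 days and not reached.

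**Effect of limited follow-up.** Assume a constant response rate, 60% responding by 60 months and no dropout. The rate is −ln(0.4)/60 = 0.01527 per month. The all-patient median is ln 2/0.01527 = 45.4 months. Among responders it is −ln(0.7)/0.01527 = 23.4 months.

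**With dropout.** Simulation of 200,000 patients per scenario. From the documents: a 1825-day dosing limit plus 56 days, giving a cap at day 1881, and a 12-week (84-day) interval that must fit before the cutoff. Assumed: exponential time to response, and 90%, 60% or 30% completing five years. Patients without response were censored at the last day on which a 12-week interval could still start. Medians in days:

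| True median | Responders only, at 90% / 60% / 30% completion | Kaplan-Meier, all patients | Shortfall |
|---|---|---|---|
| 90 | 89 / 87 / 83 | 90 | 1-8% |
| 180 | 177 / 168 / 153 | 180 | 2-15% |
| 365 | 340 / 308 / 268 | 364-367 | 7-27% |
| 730 | 534 / 478 / 399 | 727-734 | 27-46% |
| 1825 | 725 / 647 / 525 | not reached | – |

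**Duration, if censored values were entered as complete.** Assume one episode lasting at least 84 days plus an exponential part, and the same completion shares. The descriptive median was 172-179 days for a true median of 180 (1-8% censored), 306-360 for 365 (4-22% censored) and 483-698 for 730 (19-41% censored). Kaplan-Meier recovered the true value within about a day.

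The longest-interval rule works the other way. With recurring episodes (per-episode median 365 days, median gap 90 days, 60% completion; 20,000 patients), the longest episode had a descriptive median of 617 days and a Kaplan-Meier median of 715.

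**The case against.** The strongest reply is that this is a different estimand, openly stated. SAP 5.7.2.2 says the analysis is for responders, SAP 5.7.2.1 reports response rates with exact 95% CIs, and the study is descriptive with no primary efficacy endpoint. A reader therefore gets both how many respond and how fast responders do so. This stands to the extent that a responders-only summary is legitimate when labelled as conditional. It does not replace the analysis the protocol describes.

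SAP 5.2 promises Kaplan-Meier curves for time-to-event variables when there are more than 5 patients. That does not clearly restore the analysis, because 5.7.2.2 classes time to response as continuous and limits it to patients who all have the event. It is also true that SAP 5.12.6 lists only major changes and that the protocol's sentence does not name its endpoints. Replacing the stated method for a secondary endpoint still belongs under Protocol 15.5.

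Kaplan-Meier has its own weakness here. The cutoff follows the last dose, and patients may stop because they are not responding. Such censoring would be informative and could overstate eventual response. This stands and shapes the fix.

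A reader might also infer that durations are treated as complete and that both summaries are therefore biased short. The documents do not support this. The sentence after the descriptive plan adds a time-to-event analysis of duration, an exploratory Kaplan-Meier analysis of cumulative duration follows, and no text says censored values are entered as complete. Taking the longest interval also lengthens the reported duration relative to a typical episode.

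**Conclusion.** The point holds for time to response. The SAP replaces the protocol's Kaplan-Meier analysis with a responders-only descriptive summary and does not record the change. That summary ignores the response rate and runs shorter than the time to response in all treated patients. The direction follows from conditioning on response. The size rests on assumed response rates, timing and dropout: about 1-8% when response is fast, 27-46% or more when it is slow, and no Kaplan-Meier median at all where fewer than half can respond.

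For duration the point is limited to reporting. A censoring-aware analysis is already planned. The descriptive figures run short relative to Kaplan-Meier on the same variable only if censored values are entered as complete, by roughly 0-34% in the scenarios run.

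The primary safety objective is not affected.

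**What to change.** - In SAP 5.7.2.2, add a Kaplan-Meier or cumulative incidence analysis of time to response in all ITT patients, separately for NTD and TD, with the median and 95% CI. Censor non-responders at the SAP 5.7 analysis cutoff day. Because response is dated at the start of a 12- or 24-week interval, state how the last weeks before the cutoff, when no interval can still be completed, are handled.
- If Kaplan-Meier is the main analysis, add a cumulative incidence sensitivity analysis, since stopping treatment may be related to non-response.
- Keep the responders-only summary, labelled as conditional on responding.
- For duration, make the planned time-to-event analysis the main one. Show the number censored beside any descriptive statistics and say how censored values enter them.
- List any remaining departure from the protocol in SAP 5.12.6.

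The cost is SAP wording and a few more outputs, with no new data. The median time to response may be longer or not reached.
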